#### 8.3. Definition of an Adverse Event

An AE is any untoward medical occurrence in a clinical investigation subject administered a product or medical device; the event need not necessarily have a causal relationship with the treatment or usage. Examples of AEs include but are not limited to:

- Abnormal test findings;
- Clinically significant symptoms and signs;
- Changes in physical examination findings;
- Hypersensitivity;
- Progression/worsening of underlying disease
- Drug abuse;
- Drug dependency.

Additionally, they may include the signs or symptoms resulting from:

- Drug overdose;
- Drug withdrawal;
- Drug misuse;
- Drug interactions;
- Extravasation;
- Exposure during pregnancy (EDP);
- Exposure via breastfeeding;
- Medication error;
- Occupational exposure.

#### 8.4. Medication Errors

Medication errors may result, in this study, from the administration or consumption of the wrong drug, by the wrong subject, at the wrong time, or at the wrong dosage strength. Such medication errors occurring to a study participant are to be captured on the medication error

case report form (CRF) which is a specific version of the adverse event (AE) page, and on the SAE form when appropriate. In the event of medication dosing error, Pfizer should be notified immediately.

Medication errors are reportable irrespective of the presence of an associated AE/SAE, including:

- Medication errors involving subject exposure to the investigational product;
- Potential medication errors or uses outside of what is foreseen in the protocol that do or do not involve the participating subject.

Whether or not the medication error is accompanied by an AE, as determined by the investigator, the medication error should be captured on the medication error version of the adverse event (AE) page and, if applicable, any associated AE(s) are captured on an AE CRF page.

#### 8.5. Abnormal Test Findings

The criteria for determining whether an abnormal objective test finding should be reported as an AE are as follows:

- Test result is associated with accompanying symptoms; and/or
- Test result requires additional diagnostic testing or medical/surgical intervention; and/or
- Test result leads to a change in study dosing (outside of protocol-stipulated dose adjustments) or discontinuation from the study, significant additional concomitant drug treatment, or other therapy; and/or
- Test result is considered to be an AE by the investigator or sponsor.

Merely repeating an abnormal test, in the absence of any of the above conditions, does not constitute an AE. Any abnormal test result that is determined to be an error does not require reporting as an AE.

#### 8.6. Serious Adverse Events

An SAE is any untoward medical occurrence at any dose that:

- Results in death;
- Is life-threatening (immediate risk of death);
- Requires inpatient hospitalization or prolongation of existing hospitalization;
- Results in persistent or significant disability/incapacity (substantial disruption of the ability to conduct normal life functions);

• Results in congenital anomaly/birth defect.

Medical and scientific judgment is exercised in determining whether an event is an important medical event. An important medical event may not be immediately life-threatening and/or result in death or hospitalization. However, if it is determined that the event may jeopardize the subject or may require intervention to prevent one of the other AE outcomes, the important medical event should be reported as serious.

Examples of such events are intensive treatment in an emergency room or at home for allergic bronchospasm; blood dyscrasias or convulsions that do not result in hospitalization; or development of drug dependency or drug abuse.

#### 8.6.1. Protocol-Specified Serious Adverse Events

Unless the investigator believes that there is a causal relationship between study drug and an event specified below, these events should not be reported by the investigator as SAEs as described in the Serious Adverse Event Reporting Requirements section on this protocol. These events are anticipated to occur commonly in a population with LGMD2I. However, these events should still be captured as AEs in the CRF.

Protocol-specified events that will not normally be reported in an expedited manner:

- Loss of mobility or ambulation.
- Muscle weakness.
- Cardiomyopathy.
- Fracture.

Should an aggregate analysis indicate that these prespecified events occur more frequently than expected based on the expectation of frequency of the event(s) in question in the population for comparison, eg, based on epi data, literature, or other data, then this will be submitted and reported in accordance with Pfizer's safety reporting requirements. Aggregate analysis of safety data will be performed on a quarterly basis by the SMC.

#### 8.6.2. Potential Cases of Drug-Induced Liver Injury

The threshold of laboratory abnormalities for a potential case of drug-induced liver injury depends on the subject's individual baseline values and underlying conditions. Subjects who present with the following laboratory abnormalities should be evaluated further to definitively determine the etiology of the abnormal laboratory values:

• Subjects with AST or ALT and total bilirubin baseline values within the normal range who subsequently present with AST or ALT values ≥3 times the upper limit of normal (X ULN) concurrent with a total bilirubin value ≥2 X ULN with no evidence of hemolysis and an alkaline phosphatase value ≤2 X ULN or not available;

- For subjects with preexisting ALT **OR** AST **OR** total bilirubin values above the ULN, the following threshold values should be used in the definition mentioned above:
  - For subjects with preexisting AST or ALT baseline values above the normal range: AST or ALT values ≥2 times the baseline values and ≥3 X ULN, or ≥8 X ULN (whichever is smaller).

Concurrent with

• For subjects with preexisting values of total bilirubin above the normal range: Total bilirubin level increased from baseline by an amount of at least 1 X ULN or if the value reaches ≥3 X ULN (whichever is smaller).

The subject should return to the investigational site and be evaluated as soon as possible, preferably within 48 hours from awareness of the abnormal results. This evaluation should include laboratory tests, detailed history, and physical assessment.

In addition to repeating measurements of AST and ALT, laboratory tests should include albumin, creatine kinase, total bilirubin, direct and indirect bilirubin, gamma-glutamyl transferase, prothrombin time (PT)/ international normalized ratio (INR), and alkaline phosphatase and GLDH. A detailed history, including relevant information, such as review of ethanol, acetaminophen, recreational drug and supplement consumption, family history, occupational exposure, sexual history, travel history, history of contact with a jaundiced person, surgery, blood transfusion, history of liver or allergic disease, and work exposure, should be collected. Further testing for acute hepatitis A, B, or C infection and liver imaging (eg, biliary tract) may be warranted. All cases confirmed on repeat testing as meeting the laboratory criteria defined above, with no other cause for liver function test (LFT) abnormalities identified at the time, should be considered potential Hy's law cases irrespective of availability of all the results of the investigations performed to determine etiology of the abnormal LFTs. Such potential Hy's law cases should be reported as SAEs.

#### 8.7. Hospitalization

Hospitalization is defined as any initial admission (even less than 24 hours) in a hospital or equivalent healthcare facility or any prolongation to an existing admission. Admission also includes transfer within the hospital to an acute/intensive care unit (eg, from the psychiatric wing to a medical floor, medical floor to a coronary care unit, or neurological floor to a tuberculosis unit). An emergency room visit does not necessarily constitute a hospitalization; however, the event leading to the emergency room visit should be assessed for medical importance.

Hospitalization does not include the following:

- Rehabilitation facilities;
- Hospice facilities;
- Respite care (eg, caregiver relief);

- Skilled nursing facilities;
- Nursing homes;
- Same-day surgeries (as outpatient/same-day/ambulatory procedures).

Hospitalization or prolongation of hospitalization in the absence of a precipitating, clinical AE is not in itself an SAE. Examples include:

- Admission for treatment of a preexisting condition not associated with the development of a new AE or with a worsening of the preexisting condition (eg, for workup of persistent pre-treatment laboratory abnormality);
- Social admission (eg, subject has no place to sleep);
- Administrative admission (eg, for yearly physical examination);
- Protocol-specified admission during a study (eg, for a procedure required by the study protocol);
- Optional admission not associated with a precipitating clinical AE (eg, for elective cosmetic surgery);
- Hospitalization for observation without a medical AE;
- Preplanned treatments or surgical procedures. These should be noted in the baseline documentation for the entire protocol and/or for the individual subject;

Diagnostic and therapeutic noninvasive and invasive procedures, such as surgery, should not be reported as AEs. However, the medical condition for which the procedure was performed should be reported if it meets the definition of an AE. For example, an acute appendicitis that begins during the AE reporting period should be reported as the AE, and the resulting appendectomy should be recorded as treatment of the AE.

#### 8.8. Severity Assessment

If required on the AE CRFs, the investigator will use the adjectives MILD, MODERATE, or SEVERE to describe the maximum intensity of the AE. For purposes of consistency, these intensity grades are defined as follows:

MILD	Does not interfere with subject's usual function.
MODERATE	Interferes to some extent with subject's usual function.
SEVERE	Interferes significantly with subject's usual function.

Note the distinction between the severity and the seriousness of an AE. A severe event is not necessarily an SAE. For example, a headache may be severe (interferes significantly with the

subject's usual function) but would not be classified as serious unless it met one of the criteria for SAEs, listed above.

#### 8.9. Causality Assessment

The investigator's assessment of causality must be provided for all AEs (serious and nonserious); the investigator must record the causal relationship in the CRF, as appropriate, and report such an assessment in accordance with the SAE reporting requirements if applicable. An investigator's causality assessment is the determination of whether there exists a reasonable possibility that the investigational product caused or contributed to an AE; generally the facts (evidence) or arguments to suggest a causal relationship should be provided. If the investigator does not know whether or not the investigational product caused the event, then the event will be handled as "related to investigational product" for reporting purposes, as defined by the sponsor (see section on Reporting Requirements). If the investigator's causality assessment is "unknown but not related to investigational product," this should be clearly documented on study records.

In addition, if the investigator determines that an SAE is associated with study procedures, the investigator must record this causal relationship in the source documents and CRF, as appropriate, and report such an assessment in accordance with the SAE reporting requirements, if applicable.

#### 8.10. Exposure During Pregnancy

For investigational products and for marketed products, an exposure during pregnancy occurs if:

• A female becomes, or is found to be, pregnant either while receiving or having been exposed (eg, because of treatment or environmental exposure) to the investigational product; or the female becomes, or is found to be pregnant after discontinuing and/or being exposed to the investigational product;

An example of environmental exposure would be a case involving direct contact with a Pfizer product in a pregnant woman (eg, a nurse reports that she is pregnant and has been exposed to chemotherapeutic products).

• A male subject has been exposed (eg, because of treatment or environmental exposure) to the investigational product prior to or around the time of conception and/or is exposed during his partner's pregnancy.

If a study subject or study subject's partner becomes or is found to be pregnant during the study subject's treatment with the investigational product, the investigator must submit this information to the Pfizer drug safety unit on a Serious Adverse Event (SAE) Report Form and Exposure During Pregnancy (EDP) supplemental form, regardless of whether an SAE has occurred. In addition, the investigator must submit information regarding environmental exposure to a Pfizer product in a pregnant woman (eg, a subject reports that she is pregnant and has been exposed to a cytotoxic product by inhalation or spillage) using the EDP supplemental form. This must be done irrespective of whether an AE has occurred and within

24 hours of awareness of the exposure. The information submitted should include the anticipated date of delivery (see below for information related to termination of pregnancy).

Follow-up is conducted to obtain general information on the pregnancy and its outcome for all EDP reports with an unknown outcome. The investigator will follow the pregnancy until completion or until pregnancy termination) and notify Pfizer of the outcome as a follow-up to the initial EDP supplemental form. In the case of a live birth, the structural integrity of the neonate can be assessed at the time of birth. In the event of a termination, the reason(s) for termination should be specified and, if clinically possible, the structural integrity of the terminated fetus should be assessed by gross visual inspection (unless preprocedure test findings are conclusive for a congenital anomaly and the findings are reported).

If the outcome of the pregnancy meets the criteria for an SAE (ie, ectopic pregnancy, spontaneous abortion, intrauterine fetal demise, neonatal death, or congenital anomaly [in a live born, a terminated fetus, an intrauterine fetal demise, or a neonatal death]), the investigator should follow the procedures for reporting SAEs.

Additional information about pregnancy outcomes that are reported as SAEs follows:

- Spontaneous abortion includes miscarriage and missed abortion;
- Neonatal deaths that occur within 1 month of birth should be reported, without regard to causality, as SAEs. In addition, infant deaths after 1 month should be reported as SAEs when the investigator assesses the infant death as related or possibly related to exposure to investigational product.

Additional information regarding the exposure during pregnancy may be requested by the investigator. Further follow-up of birth outcomes will be handled on a case-by-case basis (eg, follow-up on preterm infants to identify developmental delays). In the case of paternal exposure, the investigator will provide the study subject with the Pregnant Partner Release of Information Form to deliver to his partner. The investigator must document in the source documents that the subject was given the Pregnant Partner Release of Information Form to provide to his partner.

#### 8.11. Occupational Exposure

An occupational exposure occurs when during the performance of job duties, a person (whether a healthcare professional or otherwise) gets in unplanned direct contact with the product, which may or may not lead to the occurrence of an adverse event.

An occupational exposure is reported to safety within 24 hours of Investigator's awareness, using the SAE Report form, regardless of whether there is an associated AE/SAE. Since the information does not pertain to a subject enrolled in the study, the information is not reported on a Case Report Form (CRF), however a copy of the completed SAE Report form is maintained in the study master file.

#### 8.12. Withdrawal Due to Adverse Events (See Also Section on Subject Withdrawal)

Withdrawal due to AE should be distinguished from withdrawal due to other causes, according to the definition of AE noted earlier, and recorded on the appropriate AE CRF page.

When a subject withdraws because of an SAE, the SAE must be reported in accordance with the reporting requirements defined below.

#### 8.13. Eliciting Adverse Event Information

The investigator is to report all directly observed AEs and all AEs spontaneously reported by the study subject's parent/legally acceptable representative. In addition, each study subject's parent/legally acceptable representative will be questioned about AEs.

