## 2. STUDY OBJECTIVES AND ENDPOINTS

## 2.1. Objectives

## 2.1.1. Primary

• To determine the safety and tolerability of multiple ascending repeat IV doses of PF-06252616 in ambulatory participants with LGMD2I.

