## 2.2. Endpoints

## 2.2.1. Primary Safety

- Incidence of dose limiting or intolerability treatment related AEs by day 337 or 561.
- Incidence, severity and causal relationship of treatment emergent AEs (TEAEs) and withdrawals due to TEAEs by day 337 or 561.
- Incidence and magnitude of abnormal laboratory findings (clinical laboratory tests [hematology, chemistry], GGT, GLDH, PT, aPTT, creatine kinase, amylase, serum ferritin, serum iron, % transferrin saturation, Total Iron Binding Capacity (TIBC), LH, FSH, estrogen, cardiac troponin I, fecal occult blood and urinalysis) by day 337 or 561.
- Abnormal and clinically relevant changes in liver MRI and physical examinations, weight, vital signs, ECG, echocardiogram measured LVEF, DXA (bone mineral density), menstruation cycle (as monitored by diary), and C-SSRS (See Appendix 1 and Appendix 2) parameters by day 337 or 561.

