## 4.1. Inclusion Criteria

Subject eligibility should be reviewed and documented by an appropriate member of the investigator's study team before subjects are included in the study.

Subjects must meet all of the following inclusion criteria to be eligible for enrollment into the study:

- 1. Male and female patients age  $\geq 18$
- 2. Diagnosis of LGMD2I as defined by clinical presentation consistent with LGMD2I and FKRP gene testing showing biallelic alterations known or likely to be pathogenic. Diagnosis must be confirmed in subject's medical history and by genetic testing obtained during routine clinical care for diagnostic purposes as reported from an appropriate regulated laboratory using a clinically validated genetic test (genetic testing is not provided by the sponsor).
- 3. Ability to walk/run 10m
- 4. Abilit to rise from chair
- 5. Adequate hepatic and renal function on screening laboratory assessments
  - $GGT \leq upper limit of normal (ULN).$
  - Alkaline phosphatase  $\leq$  ULN.
  - Total Bilirubin  $\leq$  ULN.
  - Serum Albumin  $\geq$  LLN.
  - Serum creatinine  $\leq$  ULN.
- 6. Iron content estimate on the screening liver MRI within the normal range as determined by R2\* value (R2\*  $\leq$  139 Hz at 3.0T).
- 7. Participant must provide written informed consent for participating in study.
- 8. Participant must possess the ability, per the Principal Investigator (PI), to understand and comply with protocol instruction for the entire duration of the study.

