## 4.2. Exclusion Criteria

Subjects presenting with any of the following will not be included in the study:

- 1. Known cognitive impairment or behavioral issues that would impede the ability to provide informed consent or to follow study instructions.
- 2. History of major surgical procedure within 6 weeks of signing the informed consent or planned surgery during the study.
- 3. Any injury which may impact functional testing. Previous injuries must be fully healed prior to consent. Prior lower limb fractures must be fully healed and at least 3 months from injury dates.
- 4. Previous treatment with another investigational product within 30 days or 5 half-lives, (whichever is longer) prior to consenting.
- 5. Corticosteroid treatment within 3 months prior to consenting.
- 6. Compromised cardiac function (left ventricular ejection fraction <50%).
- 7. Unwilling or unable (e.g. metal implants, requires sedation) to undergo examination with closed MRI without sedation.
- 8. History of allergic or anaphylactic reaction to a therapeutic or diagnostic protein.
- 9. Female subjects who are pregnant or nursing.
- 10. Subjects who, are biologically capable of having children who are unwilling or unable to use highly effective methods of contraception (as outlined in this protocol) during sexual activity for the duration of the study and through completion of final study visit.
- 11. Predisposition to iron accumulation. (Serum iron >1.2 X ULN, serum ferritin >1.2 ULNN).
- 12. Underlying disposition for bleeding disorder on screening laboratory assessment (PT/INR>1.25 X ULN, aPTT > 1.25 ULN, fecal occult blood is positive)
- 13. Evidence or history of clinically significant hematological, renal, endocrine, pulmonary, gastrointestinal, cardiovascular, hepatic, neurologic, or allergic disease.
- 14. Unwillingness or inability to comply with the requirements of this protocol (in the opinion of the PI) including, but not limited to, the presence of any condition (physical, mental, or social) that is likely to affect the participant's ability to return for study visits or adhere to the visit schedule.

Note: Screening laboratory tests with results considered by the investigator to be transient and inconsistent with the subject's clinical condition may be repeated once during the screening period for confirmation of eligibility.

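### The general rule for eliciting adverse events names the subject's parent or representative as informant, although every subject is a self-consenting adult

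*Protocol*

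**What the plan says.** Protocol section 8.13 (Eliciting Adverse Event Information) has two sentences. The first has the investigator report events directly observed, together with "all AEs spontaneously reported by the study subject's parent/legally acceptable representative". The second adds that "each study subject's parent/legally acceptable representative will be questioned about AEs". Neither sentence names the subject as a source.

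The population is adult. The first inclusion criterion in section 4.1, which begins "Male and female patients age", sets the lower limit at 18. The same section requires that "Participant must provide written informed consent for participating in study". Section 4.2 excludes people with "Known cognitive impairment or behavioral issues that would impede the ability to provide informed consent or to follow study instructions".

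Safety is the sole primary objective (section 2.1.1): "To determine the safety and tolerability of multiple ascending repeat IV doses of PF-06252616 in ambulatory participants with LGMD2I". Section 2.2.1 lists four primary safety items, and the first two are built on adverse events: "Incidence of dose limiting or intolerability treatment related AEs by day 337 or 561", and "Incidence, severity and causal relationship of treatment emergent AEs (TEAEs) and withdrawals due to TEAEs by day 337 or 561". SAP section 4.2.1 repeats all four.

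**The concern.** The named informant does not fit the population. An ambulatory adult who signs their own consent form will not usually attend with a parent or a legal representative. For many subjects the rule therefore points to someone who has no part in the trial.

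What is at stake is ascertainment of the adverse-event part of the primary endpoint. Many events are known first to the subject. Section 8.8 grades severity by how far the event interferes with the subject's usual function, which the subject is best placed to report. The closing telephone contact (section 6.13) consists only of adverse event monitoring and concomitant medication, so direct observation is not possible there. That call falls after the day 337 or 561 cut-off of the primary items, but it still yields safety data.

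**Working it through.** The plan states no figure that depends on the informant, and section 9.1 reports that no formal sample size calculation was made. The check is therefore a comparison of passages.

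1. **Is section 8.13 the only general elicitation rule?** Yes. The visit descriptions in section 6 and the Schedule of Activities list adverse event monitoring without saying who is asked. Section 8.1 requires observed or volunteered events to be reported but names no informant and gives no rule for questioning. Section 8.14.2 concerns recording on the case report form.

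2. **Does the informant fit the population?** No. Sections 4.1 and 4.2 together give an age of at least 18, personal written consent, and exclusion where cognition would impede consent. That a representative will not routinely exist is an inference from these criteria; the documents do not say so directly.

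3. **Does other protocol text agree with section 8.13?** Two places do not.
   - Section 1.12.2 has the subjects themselves asked about symptoms that might point to gastric erosion or haemorrhage. This conflicts with section 8.13.
   - Section 5.9 has all subjects questioned about concomitant medications at each visit. The protocol thus names the subject as informant for a parallel item but has no matching sentence for adverse events.

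4. **Does the SAP repair it?** No. SAP section 6.1 covers attribution of events to treatment, section 6.1.3 covers baseline severity and section 8.2.1.1 covers summaries. None deals with the informant.

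5. **Which primary safety items depend on the rule?**
   - Dose-limiting or intolerability treatment-related events: yes.
   - Treatment-emergent events and withdrawals due to them: yes.
   - Laboratory findings: no.
   - Liver MRI, examination, weight, vital signs, ECG, LVEF, bone density, menstrual diary and C-SSRS: no. These are measured, or obtained by their own procedures.

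   The count is two of four. Within those two, events the investigator directly observes are still captured by section 8.13 itself, and volunteered events by section 8.1. What lacks cover is systematic questioning of the subject.

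6. **Can the loss be quantified?** No. The documents give neither an expected adverse event rate nor any information on how sites question subjects in practice.

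**The case against.** The strongest reply is that this is a stray phrase with little practical effect. Adverse event monitoring is scheduled at each visit from Visit 2 onward and at the telephone contact. Subjects are watched for infusion site reactions from the start of the infusion (section 7.11) and observed for an hour afterwards (section 5.5). Staff facing a competent adult would very probably ask that adult. The wording may have been carried over from paediatric text: section 5.2 describes a concurrent paediatric Duchenne study by the same investigator, and section 12.4 mentions Duchenne advocacy groups. The documents do not state its origin, however.

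Much of this stands, and it rules out several stronger readings that a reader might infer:

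- **That subjects are never asked.** Section 1.12.2 has them asked about gastric symptoms, and section 6.15 has the investigator follow up with the subject about unresolved events after a missed visit or withdrawal. Gastric symptoms are therefore not an example of what would be lost.
- **That a site asking the subject breaks the protocol.** Section 8.13 does not restrict questioning to the representative and does not forbid asking the subject.
- **That the whole primary endpoint comes from the wrong informant.** Two of the four items do not use this rule.
- **That every adverse event assessment in all 20 subjects is compromised.** This assumes that sites apply the sentence literally, which nothing in the documents shows.

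What the reply does not remove is the text itself. Scheduled monitoring with no stated informant takes its meaning from section 8.13, and section 10 has monitors check conduct against the protocol. Good practice at the site is likely, but the plan does not secure it.

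**Conclusion.** Section 8.13 is wrong as written. It is an operative rule that feeds two of the four primary safety items, it names an informant who will not routinely exist in this population, and it conflicts with section 1.12.2. Read literally, it leaves systematic questioning of subjects unassured, so events known only to the subject could be under-ascertained.

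The direction of any error would be towards too few adverse events; its size is unknown and may be small. The conclusion rests on two assumptions: that adults meeting the consent and capacity criteria seldom have a representative involved, and that sites work from the protocol text. If sites already question subjects, the effect on the data is slight, but the text should still be corrected.

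**What to change.** In both sentences of section 8.13, replace the reference to the study subject's parent or legally acceptable representative with the study subject. Subjects' spontaneous reports are then recorded, and each subject is questioned about adverse events at the contacts where adverse event monitoring is already scheduled, including the telephone follow-up. This brings the section into line with sections 1.12.2, 4.1 and 5.9.

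The cost is a few words in one section, carried in a protocol amendment with the ethics approval that section 12.1 requires. No visit, endpoint, sample size or analysis changes, and the SAP needs no edit. A scripted, non-leading question could be added as a matter of preference, but correcting the error does not require it.
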